ClinicalTrials.gov Protocol Registration and Results System (PRS) Receipt
Release Date: May 29, 2024

ClinicalTrials.gov ID: [Not yet assigned]

Study Identification

Unique Protocol ID: IIT2023015

Brief Title: Comparison of Short-term and Long-term Outcomes of Robotic and Laparoscopic Right Colon Cancer: a 10-year Single-center Large-sample Retrospective Study

Official Title: the Ethics Committee of the First Affiliated Hospital of Nanchang University

Secondary IDs:

Study Status

Record Verification: May 2024

Overall Status: Completed

Study Start: December 1, 2014 [Actual]

Primary Completion: March 31, 2024 [Actual]

Study Completion: April 30, 2024 [Actual]

Sponsor/Collaborators

Sponsor: [name]

Responsible Party: Sponsor-Investigator

Investigator: [name] [[name]]

Official Title: the First Affiliated Hospital of Nanchang University

Affiliation: Nanchang University

Collaborators:

Oversight

U.S. FDA-regulated Drug: No

U.S. FDA-regulated Device: No

U.S. FDA IND/IDE: No

Human Subjects Review: Board Status: Exempt

Data Monitoring:

Study Description

Brief Summary: The goal of this observational study is to evaluate the short-term outcomes and long-term outcomes of robot-assisted right colon group for cancer compared

to laparoscopic-assisted right colon group. This is a large sample study based on ten years of clinical data. The main question it aims to answer is: What are the advantages of da Vinci robot right hemicolectomy compared to laparoscopic right hemicolectomy, and is there a difference in long-term efficacy between the two methods.

Detailed Description:

Conditions

Conditions: Robotic, Laparoscopic, Colon Cancer, Short-term Outcomes, Long-term Outcomes

Keywords:

Study Design

Study Type: Observational

Observational Study Model: Cohort

Time Perspective: Retrospective

Biospecimen Retention:

Biospecimen Description:

Enrollment: 1879 [Actual]

Number of Groups/Cohorts: 2

Groups and Interventions

| Groups/Cohorts | Interventions |
|---|---|
| robot-assisted right colon group Robot assisted radical surgery for right colon cancer | Device: Da Vinci Robot Surgical System Performing surgery on right colon cancer patients using the da Vinci robotic surgical system or laparoscopic surgical system Other Names: 
• Laparoscopic surgical system |
| laparoscopic-assisted right colon group Laparoscopic assisted radical surgery for right colon cancer | Device: Da Vinci Robot Surgical System Performing surgery on right colon cancer patients using the da Vinci robotic surgical system or laparoscopic surgical system Other Names: 
• Laparoscopic surgical system |

Outcome Measures

Primary Outcome Measure:

1. overall survival
[Time Frame: months]
2. disease-free survival

[Time Frame: months]

Secondary Outcome Measure:

3. the rate of postoperative complications

[Time Frame: rates]

4. operative time

[Time Frame: minute]

5. estimation of blood loss

[Time Frame: ml]

6. number of retrieved lymph nodes

[Time Frame: Number]

7. days after postoperative hospital stay

[Time Frame: day]

8. time to first exhaust

[Time Frame: hours]

9. time to liquid diet

[Time Frame: hours]

10. the rate of intracorporeal anastomosis

[Time Frame: rates]

Eligibility

Study Population: The consecutive cases of robotic-assisted or laparoscopic-assisted right colectomy between December 2014 and March 2024. All cases derived from the First Affiliated Hospital of Nanchang University.

Sampling Method: Non-Probability Sample

Minimum Age: 18 Years

Maximum Age: 85 Years

Sex: All

Gender Based:

Accepts Healthy Volunteers: No

Criteria: Inclusion Criteria:1) age: 18-85 years; 2) no distant metastasis; 3) preoperative colonoscopy showing that the tumor was located in the ileocecal region, ascending colon, hepatic flexure, or transverse colon with pathology showing malignancy; 4) signed informed consent.

-

Exclusion Criteria:1) multiple primary colorectal cancer; 2) recurrent right colon cancer; 3) preoperative neoadjuvant chemotherapy; 4) emergency surgery for intestinal obstruction, bleeding or perforation; 5) incomplete data and missing follow-up data.

-

Contacts/Locations

Central Contact Person: [name], doctor

Email: [contact]

Central Contact Backup: [name], doctor

Study Officials:

Locations:

IPDSharing

Plan to Share IPD: Undecided

Access to the database can be obtained from the corresponding author on reasonable request.

References

Citations:

Links:

Available IPD/Information:

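### Does the identical intervention entry for both cohorts leave the robotic versus laparoscopic comparison undefined?

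*Protocol*

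**What the plan says.** The Groups and Interventions table of the protocol has one row per cohort. The first is the "robot-assisted right colon group Robot assisted radical surgery for right colon cancer", the second the "laparoscopic-assisted right colon group Laparoscopic assisted radical surgery for right colon cancer". The intervention cell is the same in both rows: it is headed "Device: Da Vinci Robot Surgical System", it is described as "Performing surgery on right colon cancer patients using the da Vinci robotic surgical system or laparoscopic surgical system", and it lists the laparoscopic system as another name for that device.

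The Brief Summary puts the study question as "What are the advantages of da Vinci robot right hemicolectomy compared to laparoscopic right hemicolectomy", with a further question about long-term efficacy. Under Eligibility, the Study Population is "The consecutive cases of robotic-assisted or laparoscopic-assisted right colectomy between December 2014 and March 2024", at one hospital. There are five exclusion criteria, the last two being "4) emergency surgery for intestinal obstruction, bleeding or perforation; 5) incomplete data and missing follow-up data". None of the five concerns conversion or a change of technique. Study Design gives "Enrollment: 1879 [Actual"]" with no split by cohort, and Study Status marks the study as completed.

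**The concern.** Robotic versus laparoscopic surgery is the only contrast in this study, so the exposure should be the most clearly written item in the record. Instead, the laparoscopic cohort is entered under the robot's name, the comparator appears as an alias of the robot, and either technique satisfies the description in either row.

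The worry then extends to cases that switch. Suppose an operation begins robotically and is finished laparoscopically. If such cases were filed by the technique that completed the operation, the more difficult robotic starts would leave the robotic cohort and join the comparator. Short-term outcomes, and possibly survival, would then look better for the robot than they are. Classification in a retrospective study happens after outcomes are known, so an open rule on cohort membership deserves a second look.

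**Working it through.** **Step 1: does the document separate the cohorts?** The relevant fields compare as follows.

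| Field | Robotic cohort | Laparoscopic cohort | Separates them? |
|---|---|---|---|
| Cohort label | robot-assisted | laparoscopic-assisted | yes |
| One-line description | robot-assisted radical surgery | laparoscopic-assisted radical surgery | yes |
| Intervention name | da Vinci | da Vinci | no, and wrong for the second cohort |
| Intervention description | either system | either system | no |
| Brief Summary | da Vinci right hemicolectomy | laparoscopic right hemicolectomy | yes |
| Study Population | robotic-assisted cases | laparoscopic-assisted cases | yes |

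Only the intervention cell fails. Its wording describes the study as a whole, which is what one intervention record linked to both groups would look like. No reader of the other four fields would assign a laparoscopic operation to the robotic group.

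**Step 2: does the duplicate cause the switched-case gap?** Suppose the entries were corrected, with da Vinci in one row and laparoscopic in the other. A case begun with one and finished with the other would still be unplaced. The gap therefore exists with or without the duplicate. A case finished open fits neither entry, since neither mentions open surgery. The document has no rule that files cases by completed technique.

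**Step 3: how large could a filing effect be?** The document gives no conversion rate, complication rate or cohort split, so every input here is assumed apart from the total of 1879:

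- 600 robotic and 1,279 laparoscopic starts (600 + 1,279 = 1,879);
- the same share *s* of switched cases in both cohorts;
- complication risk 40% in switched cases and 20% in the rest.

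Filed as started, both cohorts have risk 0.20 + 0.20*s*, which is 20.6%, 21.0% and 22.0% for *s* = 3%, 5% and 10%. The true difference is zero.

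*(a) Robotic switches refiled as laparoscopic; laparoscopic switches kept.* The robotic rate becomes 20.0%. The laparoscopic rate is [1,279 × (0.20 + 0.20*s*) + 600*s* × 0.40] / (1,279 + 600*s*):

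- 3%: (263.47 + 7.2) / 1,297 = 20.9%, difference 0.9 points
- 5%: (268.59 + 12) / 1,309 = 21.4%, difference 1.4 points
- 10%: (281.38 + 24) / 1,339 = 22.8%, difference 2.8 points

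*(b) Completed technique applied to both cohorts, with laparoscopic switches going to open surgery and so leaving.* The laparoscopic rate is [1,279(1 − *s*) × 0.20 + 600*s* × 0.40] / [1,279(1 − *s*) + 600*s*]:

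- 3%: (1,240.63 × 0.20 + 18 × 0.40) / 1,258.63 = 20.3%, difference 0.3 points
- 5%: (1,215.05 × 0.20 + 30 × 0.40) / 1,245.05 = 20.5%, difference 0.5 points
- 10%: (1,151.1 × 0.20 + 60 × 0.40) / 1,211.1 = 21.0%, difference 1.0 points

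*(c) All switches in both cohorts go to open surgery and are dropped.* Both rates are 20.0% and the difference is zero.

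*(d) Robotic cases kept as started; laparoscopic switches dropped.* The robotic rates stay at 20.6%, 21.0% and 22.0% against 20.0%, a false difference of 0.6, 1.0 and 2.0 points *against* the robot.

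Scenario (a) depends on treating the two cohorts differently. Under equal treatment in (b) the effect is about a third as large, in (c) it vanishes, and in (d) it changes sign.

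**The case for a change.** The strongest reply is that cohort membership is the exposure definition in a retrospective cohort study and so belongs in the group description, not in an analysis plan. The label robot-assisted does not say whether it means started or completed robotically, and the one field that could have said so admits both systems in both rows. The correction would also be cheap in words: two entries and one sentence.

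Part of this stands. The intervention entry is wrong for the laparoscopic cohort and contradicts that cohort's label, and the record would be clearer if it stated whether membership follows starting or completed technique. But a correct device name would not answer the second question. Counting a case in the cohort where it began is a familiar convention that analysts can apply without an instruction here, and nothing in the protocol points to the opposite practice. Nor is the cost wording alone: tracing switched cases could mean going through operative notes for up to 1,879 patients in a finished study, for an effect whose size and sign the document cannot establish.

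**Conclusion.** No change to the plan is called for. The shared intervention entry is a registry slip. It can be tidied by matching each device to its cohort, but the comparison is already readable from four other places in the same document, so the correction reassigns no patient and alters no estimate.

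The missing statement on switched cases is a gap of detail that analysts, or an analysis plan not at hand, can fill sensibly. A firm claim of bias favouring the robot is not supported. On assumed inputs (600 and 1,279 starts, 3% to 10% switched, 40% against 20% risk) the false difference in complications runs from 2.8 points in the robot's favour to 2.0 points against it, according to how each cohort's switches are filed. Only complications were worked through; for operative time, blood loss and survival the document offers nothing from which to derive a direction. The conclusion would need to be revisited if an analysis plan or data dictionary showed that cases were in fact filed by completed technique in one cohort only.

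### Do the unit-only time frames and the undefined missing-follow-up exclusion leave overall and disease-free survival unusable?

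*Protocol*

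**What the plan says.** Under Outcome Measures the protocol lists two primary and eight secondary outcomes, each with a time-frame entry. Overall survival and disease-free survival both read "Time Frame: months". The complication rate and the intracorporeal anastomosis rate read "Time Frame: rates", and the lymph node count reads "Time Frame: Number". The other five hold minutes, millilitres, days or hours. None of the ten gives a starting point, a length of observation or an end, and the Detailed Description is empty.

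Under Eligibility, the study population is consecutive cases of "right colectomy between December 2014 and March 2024", and the fifth exclusion criterion removes "incomplete data and missing follow-up data". It names no minimum follow-up and does not separate short follow-up, loss to follow-up and no contact at all.

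Study Status gives primary completion as 31 March 2024 and study completion as 30 April 2024. The text ties neither date to a survival outcome. Enrolment is an actual count of 1879, and the study is recorded as completed.

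**The concern.** A time-to-event outcome needs an origin and a last follow-up date, and a unit supplies neither. That gap meets an eligibility rule that selects patients on something known only after surgery. Operations run to the month of primary completion, so many patients have short potential follow-up. If the exclusion removed event-free patients whose follow-up was short or broken off, while patients who had died or relapsed stayed in, the remaining cohort would be enriched for events and the survival estimates would be too low. A statistical analysis plan could not repair this, because the patients would already be outside the cohort. The complication rate has a milder form of the same problem, since no window is stated.

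**Working it through.** **Which entries matter.** Of the ten, seven (outcomes 4 to 10) are fixed at surgery or are themselves a duration or count in the hospital stay: operative time, blood loss, nodes, stay, first exhaust, liquid diet, intracorporeal anastomosis. A unit in the wrong field does no harm there. Overall survival, disease-free survival and complications remain.

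**Potential follow-up.** From 1 December 2014 to 31 March 2024 is 3408 days (3409 counting both ends), or 3408/30.4375 = 112 months. With a cut-off at 31 March 2024, potential follow-up runs from 0 to 112 months. Under uniform accrual (an assumption), 36/112 = 32.1% of patients (about 604 of 1879) cannot reach 36 months, and 60/112 = 53.6% (about 1007) cannot reach 60. This is ordinary staggered entry, which Kaplan-Meier and Cox methods handle by censoring.

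**Complication window.** 31 March 2024 plus 30 days is 30 April 2024, so every eligible patient can complete 30 days by study completion. For 90 days, operations after 31 January 2024 fall short: 60/3409 × 1879 = about 33 patients, 1.8%.

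**Three readings of the exclusion.** Further assumptions, none of them in the document: true five-year survival 75%, so S(t) = exp(−kt) with k = −ln(0.75)/60 = 0.004795 per month, and loss unrelated to outcome.

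1. Only patients with no contact at all are removed. The estimate stays at 75.0%, because removal does not depend on outcome.

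2. Patients lost before the cut-off are removed instead of censored. Let a proportion p be lost by 60 months, with loss survival SL(t) = (1−p)^(t/60), and G(t) = 1 − t/112. The hazard among those retained is k·S(t)·G(t)·SL(t) divided by the integral from t to 112 of [k·S·G + S/112]·SL. Accumulating it to 60 months gives:

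| Lost by 5 years | 5-year survival | Shift from 75.0% |
|---|---|---|
| 5% | 74.3% | −0.7 points |
| 10% | 73.6% | −1.4 points |
| 20% | 72.1% | −2.9 points |

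3. Event-free patients who cannot reach a fixed horizon are removed. For 60 months, the share able to reach it is 52/112 = 0.4643. The share operated on too late but dying within their own follow-up is the integral from 0 to 60 of (1−S(u))/112 = 0.0702. The estimate is 0.4643 × 0.75/(0.4643 + 0.0702) = 65.2%, or 52.8% to 70.1% for linearly rising to falling accrual.

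**Which reading the text supports.** The third needs a horizon, and the protocol states no horizon, landmark or minimum follow-up. It also sits badly with consecutive cases to March 2024: with a five-year horizon, patients operated on after about March 2019 would remain only if they had died. Follow-up that is short because surgery was recent is not missing. The first two readings are the natural ones, and only the second moves the estimate.

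**Effect on the comparison.** The long-term question under Study Description is whether the two methods differ. With the same accrual and loss in both groups and no true difference, the same distortion applies to each, so the hazard ratio stays at 1.

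**The case for a change.** The strongest case for a change is that this is more than detail left to an analysis plan. The time-frame fields belong to this document and are filled with the wrong kind of content. The exclusion is an eligibility rule that decides who is in the cohort, and the stated aim concerns long-term efficacy. The neutral hazard ratio also depends on equal accrual and loss, and the protocol gives neither by group. Under the third reading, the same true survival gives 52.8% with rising accrual and 70.1% with falling accrual, so groups that accrued differently could show a false difference.

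The textual part stands: the entries are wrong in kind and the exclusion is undefined. The possibility of a false difference also stands in principle, but only under the reading the text supports least, and with accrual patterns that would have to be assumed. What remains is an unwritten definition with an ordinary default. Because the study is complete, writing a preferred censoring rule into the record could make it misstate what was done. The rule actually applied, and the number removed in each group, are matters for reporting the results.

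**Conclusion.** No change to the plan follows. Seven of the ten time-frame entries are harmless. For overall survival, disease-free survival and complications, the unit in the period field is a clerical slip, and the missing origin, censoring time and window are details an analyst would fill in the usual way. The undefined exclusion is the only part with a route to bias. On its natural readings the effect on absolute five-year survival runs from nothing to a fall of 0.7 to 2.9 points. That range assumes 75% five-year survival, a constant hazard, uniform accrual to 31 March 2024 and 5 to 20% loss unrelated to outcome. The fall to 65.2% needs a horizon the protocol never states and should carry little weight. No bias in the robotic versus laparoscopic comparison is shown. That would change only with evidence that event-free patients were removed for incomplete follow-up and that this happened unequally between the groups, and the protocol contains none.

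### Does the unit entered as the time frame for postoperative complications leave the comparison open to uneven capture?

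*Protocol*

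**What the plan says.** The Outcome Measures section of the protocol names two primary and eight secondary outcomes, each with a time-frame field. The entries are:

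- Overall and disease-free survival (outcomes 1 and 2): "Time Frame: months"
- Postoperative complications, worded as "the rate of postoperative complications", and intracorporeal anastomosis (3 and 10): "Time Frame: rates"
- Operative time (4): "Time Frame: minute"
- Blood loss (5): the unit ml
- Lymph nodes retrieved (6): "Time Frame: Number"
- Postoperative stay (7), worded as "days after postoperative hospital stay": "Time Frame: day"
- Time to first exhaust and time to liquid diet (8 and 9): "Time Frame: hours"

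None of the ten is a period. The Brief Summary separates short-term from long-term outcomes without attaching a length to either, and the Detailed Description is blank. The study is retrospective and from a single centre. It covers operations from December 2014 to March 2024, was completed on 30 April 2024, and has 1879 patients.

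**The concern.** For most of these outcomes the missing period does no harm. A complication rate is different: it is the proportion of patients with an event by some time, and it has no definite value until that time is given. Two readings of an open window could treat the groups unequally.

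- **Counting to discharge.** Observation ends when the patient goes home. Postoperative stay is itself a compared outcome, so the group that leaves sooner would have fewer days in which an event could be recorded.
- **Counting over all follow-up.** Time at risk would depend on the date of surgery. If one technique was used more in later years, its patients would have had less time to accumulate events.

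Either could make one technique look safer when the true risks are equal. The study's main question concerns the advantages of robotic surgery, and complications are its direct measure of postoperative harm. Because the data already exist, an open window also leaves room to choose it after seeing them.

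**Working it through.** The protocol states no figure on this point, so there is nothing to reproduce. Three checks apply.

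**1. Does any field or other text give a window?** Fields with a time window: 0 of 10. The rest of the protocol supplies none for complications.

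**2. How far could observation time vary?** Inputs are the dates in Study Status and Eligibility, taking 1 December 2014 as the first and 31 March 2024 as the last possible day of surgery.

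- Last possible operation to study completion: 31 March to 30 April 2024 = 30 days.
- First possible operation to study completion: 1 December 2014 to 30 April 2024 = 3438 days, and 3438 / 365.25 = 9.4 years.
- Ratio: 3438 / 30 = 115.

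So an unlimited window would be very uneven between patients. It would bias the comparison only if the two techniques were spread differently over the calendar, and the document does not say whether they were. The same dates show that every patient could have a full 30-day window, while a 90-day window could not be completed for the latest operations.

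**3. How large could a counting-to-discharge artefact be?** Every input here is assumed: a true 30-day risk of 20% in both groups, exponential onset times with mean m days, and the same stay of L days for everyone in a group. The share of 30-day complications arising by day L is

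(1 − exp(−L/m)) / (1 − exp(−30/m)).

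With m = 7:

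- L = 7: share 0.641, recorded rate 20% × 0.641 = 12.8%.
- L = 9: share 0.734, recorded rate 20% × 0.734 = 14.7%.
- Difference 1.9 points (1.85 before rounding), ratio 0.87.

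Across m = 5, 7 and 10:

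| Stays compared (days) | m = 5 | m = 7 | m = 10 |
|---|---|---|---|
| 6 vs 8 | 2.0 points, ratio 0.88 | 2.1 points, ratio 0.84 | 2.1 points, ratio 0.82 |
| 7 vs 9 | 1.6 points, ratio 0.90 | 1.9 points, ratio 0.87 | 1.9 points, ratio 0.85 |
| 7 vs 10 | 2.2 points, ratio 0.87 | 2.6 points, ratio 0.83 | 2.7 points, ratio 0.80 |

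The range is 1.6 to 2.7 points. If the stays are equal, the two shares are equal and the difference is zero. The whole effect therefore comes from the assumed gap in stay, for which the protocol gives neither size nor direction.

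The model also leaves out two features that would shrink the artefact. A patient with a complication tends to stay longer, so discharge is not independent of the event as the formula supposes. And a readmission to the same hospital can appear in the same records. The range shows what could happen under one crude reading; it does not estimate bias in this study.

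**The case for a change.** The strongest case for a change is that this is not a detail left for later. The protocol has a field for exactly this information and fills it with the wrong kind of content. Without a period the complication rate is not fully defined, and in a retrospective study several definitions can be tried on data already in hand. The repair looks cheap, since 30 days after surgery fits the stated dates even for the last possible patient.

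Much of this stands. The entry is wrong and the window is unstated. What does not stand is the step from a misfilled field to uneven capture. The document does not describe how complications were ascertained, states no expected difference in stay, and does not say which technique came later. The nine-year reading is also strained: the Brief Summary puts short-term outcomes apart from long-term ones and frames the long-term question as one of efficacy, with survival and disease-free survival as the primary outcomes. Postoperative complications belong most naturally with the short-term group.

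Nor is the repair as cheap as it looks if it means imposing a window rather than naming the one used. Should the data have come from inpatient charts only, a 30-day count would require post-discharge review for up to 1879 patients over nearly ten years, and events treated elsewhere might not be recoverable.

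**Conclusion.** The observation about the fields is correct, but it does not amount to a fault that calls for a change. The plan sets no rule that produces a wrong complication rate; it omits a detail that analysts would ordinarily supply by applying one conventional short-term window to every patient. The dates allow such a window of 30 days. A count limited to the hospital stay would also be a recognisable definition, provided that the report names it and reads the comparison with that limit in mind.

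The other nine entries are clerical. Operative time, blood loss, node count and type of anastomosis are settled at surgery or pathology. Stay, first exhaust and liquid diet are durations with a natural start and end. The survival outcomes run to the end of each patient's follow-up. Rewording these fields would change no result.

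The 1.6 to 2.7 points rest wholly on the assumed risk, onset distribution and stays, so they are an illustration and not a finding about this study. The conclusion would differ if there were evidence that complications were counted over unequal periods in the two groups. The protocol contains none.

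### Does requiring signed informed consent in a retrospective, exempt cohort remove the patients who died and so bias overall and disease-free survival?

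*Protocol*

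**What the plan says.** Under Eligibility, the fourth inclusion criterion is "4) signed informed consent". It does not say what the patient consented to, or when. Four other entries bear on how it should be read:

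- Study Design: "Time Perspective: Retrospective".
- Oversight: "Human Subjects Review: Board Status: Exempt".
- Study Population: "The consecutive cases of robotic-assisted or laparoscopic-assisted right colectomy between December 2014 and March 2024".
- Primary Outcome Measure: "1. overall survival" and "2. disease-free survival".

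The record was released in May 2024 with the study marked as completed, and it gives "Enrollment: 1879 [Actual]". It does not mention a waiver of consent, contact with past patients, or any handling rule for patients who had died.

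**The concern.** In a prospective trial a consent criterion is routine, because consent comes before time zero. Here the cases go back almost ten years and the work was done from records. If consent to this study was needed, a patient operated on in 2015 could give it only if alive and reachable when the study was set up. Entry would then depend on surviving to a date after surgery, so the primary event itself would cause exclusion. No later analysis recovers patients removed at entry, so this could not be left to a statistical analysis plan.

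Two things would be at stake. Absolute overall and disease-free survival would be inflated. And if the robotic share of operations changed over the decade, the two groups would have different intervals from surgery to consent, so the inflation would differ between them and could create a difference where none exists.

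The exempt status adds to the unease: a study exempt from board review would not obviously be collecting individual study consent.

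**Working it through.** The protocol gives no event count, survival rate, accrual by year or group sizes, so it has no figure to reproduce. The question is what each reading of the criterion would do.

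**Inputs from the protocol.** Accrual from December 2014 to the end of March 2024, which is 112 months; 1,879 patients, used only as a scale.

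**Assumptions.** Constant hazard; 5-year survival of 65%, 75% or 85%; identical true survival in both groups; study consent sought at month T from December 2014. T = 97 (January 2023) and T = 60 are used for illustration. The protocol states neither.

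**Step 1: deaths by the cut-off, uniform accrual.** λ = −ln(S5)/60. Share dead = 1 − (1 − e^(−112λ))/(112λ).

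At 75%: λ = 0.004795, 112λ = 0.5370, share = 1 − 0.4155/0.5370 = 22.6%, or 425 per 1,879. At 65% and 85% the shares are 31.3% (588) and 13.7% (258).

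**Step 2: deaths lost if consent is sought at month T.** Share of patients lost = (T/112) × [1 − (1 − e^(−λT))/(λT)].

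- T = 97, 75%: 0.866 × 0.2003 = 17.3%, about 326 per 1,879. As a share of deaths, 17.3/22.6 = 77%. The range over 65–85% survival is 76–77%.
- T = 60, 75%: 0.536 × 0.1310 = 7.0%, which is 31% of deaths.
- T at the March 2024 cut-off: every death is lost.

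Simulated Kaplan-Meier 5-year survival among those kept, T = 97 and uniform accrual, rises from 65% to 91%, from 75% to 94%, and from 85% to 97%.

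**Step 3: the comparison between groups.** Patients operated on before T are kept with probability e^(−λ(T−u)), where u is the month of surgery, and their time from u to T is event-free by construction. The apparent death rate, as a fraction of the true one, is therefore the person-time after the later of u and T divided by all person-time among those kept. Integrating over accrual at T = 97 and 75% survival gives 0.26 for uniform accrual, 0.37 for accrual rising linearly from zero, and 0.20 for accrual falling linearly to zero. The false rate ratios are:

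| Accrual in the two groups | Rate ratio, true value 1.0 |
|---|---|
| Same pattern | 1.0 |
| One rising, one uniform | 0.37/0.26, about 1.4 |
| One rising, one falling | 0.37/0.20, about 1.8 |

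**Step 4: the other reading.** If consent was signed before surgery, whether to the operation alone or also to later research use of the records, it precedes time zero. No patient is lost through having died, every quantity in Step 2 is zero, and the ratio in Step 3 is 1.0 whatever the accrual pattern.

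**Step 5: which reading the text supports.** Sampling consecutive cases is hard to square with keeping only those alive at a later date. A retrospective design with exempt status suggests that old cases were not being approached for consent. Nothing in the document describes such an approach. The context therefore favours Step 4, or at worst leaves the two readings level.

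**The case for a change.** The strongest case for acting is that the document permits the harmful reading and never rules it out. The identifier, IIT2023015, is compatible with set-up around 2023, when early patients could consent only if they had survived. On the harmless reading the criterion excludes hardly anyone, which makes one wonder why it is there. The downside is severe, the study is finished so the investigators know what they did, and one line would settle the matter. The exclusion of patients with missing follow-up is already one selective filter on the survival cohort.

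Some of this stands. The term is undefined, the arithmetic is right under its assumptions, and inflation of absolute survival would not need any imbalance between groups. But an identifier does not date a consent form, and a criterion that excludes almost nobody is common in eligibility lists. Exempt status and a consent criterion are in tension without contradicting each other, and exempt status is at least as much a sign that study consent was not being collected. The largest ratio, 1.8, needs study consent, a late consent date and opposite accrual trends all at once, and the protocol supplies none of the three.

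**Conclusion.** The concern does not hold as a defect of the plan. It shows what would happen under one reading of an undefined term, and the document does not adopt that reading. If study consent had been sought after surgery, the effect on absolute survival could be large: 31% to 77% of deaths lost at 75% 5-year survival for the two illustrative dates, and all of them if consent was sought at the cut-off. The comparison between groups, which is the study's stated question, would be distorted only if accrual timing or mortality before consent also differed by group, with a rate ratio of 1.0 to 1.8 across the patterns tried at January 2023. If consent was signed around the operation, the effect is zero and deleting the criterion would change no result.

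Following the protocol as written is therefore not shown to give a wrong answer. This is missing detail of low severity: which consent was meant and when it was signed, which the investigators can state in their report. The conclusion rests on the surrounding entries and would change if it emerged that patients were excluded for lack of consent obtained after surgery.
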